#### **2.8.1 Adverse events (AEs)**

All treatment emergent adverse events starting on or after the first dose of study treatment and until the last dose of study treatment plus 7 days (30 days for serious adverse events [SAEs]) will be included in all summaries and listings. Adverse events occurring after signing of informed consent but before first dose of study treatment and those occurring after 7 days of last study treatment (30 days for SAEs) will be listed only.

All adverse events will be coded using the MedDRA dictionary and summarized by system organ class and preferred term using frequency and percentage.

Primary system organ classes will be sorted alphabetically and, within each primary system organ class, the preferred terms will be sorted in descending order of frequency.

If a patient reported more than one adverse event with the same preferred term, the adverse event will be counted only once. If a patient reported more than one adverse event within the same primary system organ class, the patient will be counted only once at the system organ class level.

In addition following information will be listed by treatment group:

- Severity grade
- Relationship to the study treatment
- Duration
- Whether it constitutes a serious adverse event
- Action taken regarding study treatment
- Concomitant medication(s) taken or non-drug therapies given
- Outcome

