7.1 Adverse events

An adverse event (AE) is any untoward medical occurrence (i.e., any unfavorable and unintended sign [including abnormal laboratory findings], symptom or disease) in a patient or clinical investigation subject *after providing written informed consent* for participation in the study. Therefore, an AE may or may not be temporally or causally associated with the use of a medicinal (investigational) product. Study treatment includes the study drug under evaluation and the comparator treatment or placebo that is given during any phase of the study. Medical conditions/diseases present at the time of screening are only considered AEs if they worsen after the subject has signed informed consent.

For all subjects who sign informed consent and who are randomized into the Double-blind Treatment Period of the study will have all adverse events that occur **after informed consent is signed** recorded on the Adverse Event CRF.

The occurrence of adverse events should be sought by non-directive questioning of the subject at each visit during the study. Adverse events also may be detected when they are volunteered by the subject during or between visits or through physical examination, laboratory test, or other assessments.

Abnormal laboratory values or test results constitute adverse events only if they fulfill at least one of the following criteria:

- they induce clinical signs or symptoms;
- they are considered clinically significant; and/or
- they require therapy.

Clinically significant abnormal laboratory values or test results should be identified through a review of values outside of normal ranges/clinically notable ranges, significant changes from baseline or the previous visit, or values which are considered to be non-typical in subject with underlying disease. Investigators have the responsibility for managing the safety of individual subject and identifying adverse events. Alert ranges for labs and other test abnormalities are included in [Appendix 1](#).

Adverse events should be recorded in the Adverse Events eCRF under the signs, symptoms or diagnosis associated with them, accompanied by the following information:

- Severity grade
 - mild: usually transient in nature and generally not interfering with normal activities
 - moderate: sufficiently discomforting to interfere with normal activities
 - severe: prevents normal activities
- Relationship to the study treatment
- Duration (start and end dates or if continuing at final exam)

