- Whether it constitutes a serious adverse event (SAE - See [Section 7.2](#) for the definition of SAE)
- Action taken regarding study treatment
- Concomitant medication(s) taken or non-drug therapies given
- Outcome.

Once an adverse event is detected, it should be followed until its resolution or until it is judged to be permanent. An assessment should be made at each visit (or more frequently, if necessary) of any changes in severity, the suspected relationship to the study treatment, the interventions required to treat it, and the outcome.

Information about common side effects already known about the study drug can be found in the Investigator Brochure (IB) or will be communicated between IB updates in the form of Investigator Notifications (INs). This information will be included in the subject informed consent and should be discussed with the subject during the study as needed.

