9.5.2 Safety variables

The assessment of safety will be based mainly on the frequency of adverse events and laboratory data. Other safety data (e.g., vital signs and special tests) will be considered, as appropriate.

Adverse events will be summarized by presenting, for each treatment group, the number and percentage of subjects having any adverse event, having an adverse event in each body system and having each individual adverse event. Any other information collected (e.g., severity or relatedness to study medication) will be listed, as appropriate.

Adverse events and serious adverse events up to and including the Week 12 visit will be included in the database for the analysis at the primary analysis time point (Week 12).

Laboratory variables will be summarized.

Analysis of safety data will be based on the Safety Set.

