## 2.4.2 Prior, concomitant and post therapies

Prior or concomitant medication will be identified based on recorded or imputed start and end dates of medication taken, as follows:

**Prior medication:** Treatments taken and stopped prior to first dose of study treatment.

**Concomitant medication:** Any medication administered at least once between the day of first dose of randomized study treatment and the last day of study visit (including those which were started pre-baseline and continued into the treatment period), other than study medication, will be considered as concomitant medication.

Concomitant medications excluding tropical corticosteroid will be summarized.

Medications will be identified and presented in alphabetical order, using Novartis drug and therapy dictionary (NovDTD) and by Anatomical Therapeutic Chemical (ATC) codes and grouped by anatomical main group (the first level of the ATC codes).

Prior, concomitant medications will be summarized by treatment using frequency counts and percentages for Safety Set, in separate tables.

Tables will also show the overall number and percentage of subjects receiving at least one drug of a particular ATC code and at least one drug in a particular anatomical main group. In addition, concomitant use of tropical corticosteroid will be summarized separately by treatment.

Treatment use for indication, dose and date of administration will be listed. Duration of exposure will be presented by treatment if treatment is stopped during study period. Ongoing treatments will be flagged.

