## 4 Change to protocol specified analyses

Missing data will not be imputed using last-observation-carried-forward (LOCF) method for primary efficacy variable, since there is only one post-baseline visit.

For continuous secondary efficacy variables with more than one post-baseline assessment, missing data will be imputed using multiple imputation (in addition to LOCF).

For cardiometabolic biomarker, if the normality assumption is not tenable, additionally data will be analyzed using stratified Wilcoxon rank sum test.

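### SAP 2.8.1 selects adverse events for the tables by onset date alone, so an event that starts in screening and worsens on treatment can be left out of the AE and SAE tables

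*SAP*

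**What the plan says.** SAP 2.8.1 sets the selection rule in two sentences. The first admits to the summaries "All treatment emergent adverse events starting on or after the first dose of study treatment", with an end limit of 7 days after the last dose for AEs and 30 days for SAEs. The second takes "Adverse events occurring after signing of informed consent but before first dose of study treatment", together with events beyond the end limit, and sends them to the listings only. The SAE subsection that follows describes a table by system organ class and preferred term and adds no rule of its own on onset or worsening.

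On data collection, protocol 7.1 records AEs of randomized subjects from consent onward. Of pre-existing illness it says: "Medical conditions/diseases present at the time of screening are only considered AEs if they worsen after the subject has signed informed consent". Among the items recorded for each AE are a severity grade and "Duration (start and end dates or if continuing at final exam" (the bracket closes there). On follow-up it says: "Once an adverse event is detected, it should be followed until its resolution or until it is judged to be permanent", with changes in severity reviewed at each visit. Protocol 7.2.1 includes worsening of something pre-existing in its definition of an SAE.

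**The concern.** Treatment-emergent events are commonly understood to include events that were present before dosing and got worse afterwards. SAP 2.8.1 uses the term but ties it to the start date. Deterioration that happens on study drug, in an event first seen during screening, is then classed with pre-treatment events and does not count in either arm's AE or SAE percentage.

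This would matter for a drug whose known risks include aggravation of existing illness. Protocol 3.6 describes exacerbations of inflammatory bowel disease on secukinumab, some of them serious. Whether such a case is tabulated should depend on what happened after dosing, and not on when the event was first written down.

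**Working it through.** No arithmetic applies. The documents give no rate for screening-onset AEs or for their worsening, so the number affected cannot be calculated. The check is to run each kind of case through the two sentences of SAP 2.8.1.

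1. **AE that starts on or after first dose.** It meets the first sentence and is tabulated.

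2. **Condition present at screening that first worsens after first dose.** Under protocol 7.1 it becomes an AE only on worsening. By inference its start date is the date of worsening, so it is tabulated. The documents do not state the dating rule.

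3. **AE that starts between consent and first dose and becomes more severe after dosing.** This splits on how it is recorded.
   - If a new record is opened with the date of worsening, it meets the first sentence and is tabulated.
   - If it stays on its original record with its original start date, it fails the first sentence and meets the second. It is listed only.
   - A condition that first worsens during screening, and so is already an AE before dosing, falls here too if it worsens again on treatment.

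4. **Non-serious AE that starts before first dose and becomes serious after it.** The wording of protocol 7.2.1 would allow it to be treated as an SAE arising at the worsening. If so dated, it is tabulated. If seriousness is only updated on the existing record, it appears in the SAE listing but not in the SAE table.

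5. **Event already serious before first dose that progresses after it.** Protocol 7.2.2 has progression reported as follow-up to the original episode. That governs the paper SAE form and does not settle how the clinical database dates the event.

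Next, does anything elsewhere close the branch in case 3?

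- Protocol 7.1 follows each AE to resolution and reviews its severity at visits, but does not ask for a new record when severity rises. This is compatible with one record per event and does not prove it.
- SAP 5.1.1 imputes partial AE start and end dates. It has no date of worsening.
- SAP 4, on departures from the protocol analyses, does not mention AEs.
- SAP 6 cites a safety Master Analysis Plan, and the SAP document history records a 2017 update made for consistency with that type of plan, including the safety specification. SAP 2.8.1 does not refer to it for this definition, and its content is not available here.

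So the omission follows from the text of 2.8.1 whenever the event keeps its original record. Whether events do so is not shown.

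**The case against.** The strongest reply is that the gap depends on a data-handling convention the documents do not show. If the eCRF opens a new record on worsening, nothing is lost. The Master Analysis Plan may also define treatment emergent to include worsening, and the document history shows that the SAP was deliberately brought into line with it. This stands as a limit on the point. It does not remove it: 2.8.1 qualifies the term with a start-date condition, and a programmer working from the SAP alone would apply that condition.

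The reply on serious events also largely stands. Because protocol 7.2.1 counts worsening, an AE that newly becomes serious may well be dated at that moment, so the SAE part of the point is weaker than the AE part.

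The effect on the tables is narrow. Each subject counts once per preferred term and once per organ class. Severity is listed and not tabulated. Eligibility rules on infection, uncontrolled disease and significant findings limit what can be ongoing at first dose.

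A reader might infer more from three things, and the documents do not support it.

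- Protocol 9.5.2 plans the AE table with no onset limit, which could suggest that the SAP departed from the protocol without declaring it. That section is a general description, and a treatment-emergent window is ordinary elaboration. The fix proposed here keeps such a window.
- SAP 2.4.2 counts medication "including those which were started pre-baseline and continued into the treatment period", which could suggest inconsistent treatment of AEs. That rule is about mere continuation. Its AE counterpart would tabulate everything ongoing at first dose, which nobody would want.
- The omission could be read as favouring secukinumab. The rule is the same in both arms, and nothing in the documents fixes the direction of any effect.

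**Conclusion.** The point holds as a narrow, conditional flaw of low severity. SAP 2.8.1 states an onset-only rule with no worsening clause, and an AE that starts before first dose, worsens after it and keeps its original record is left out of the tables.

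The conclusion rests on two assumptions that the documents neither confirm nor exclude: that worsening does not open a new eCRF record, and that the programming follows 2.8.1 as written and not a wider definition in the Master Analysis Plan.

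The size cannot be estimated. It is probably very small, because it needs an AE that begins in screening, is still present at first dose and then deteriorates. The most that changes is a subject's presence or absence under a preferred term, an organ class or the overall count, and at the higher levels nothing changes if the subject has another qualifying event. No hypothesis test uses these tables. It would be wrong to conclude that on-treatment deterioration goes unreported: the listings carry severity, seriousness, action taken and outcome, and the laboratory shift tables and notable vital signs pick up some of it.

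**What to change.** In SAP 2.8.1, define a treatment-emergent AE as one that either starts on or after first dose, or starts before first dose and increases in severity or becomes serious on or after it, within the existing end limits. Apply the definition to both the AE and the SAE tables. Align it with the safety Master Analysis Plan; if that plan already has such a definition, quote it in 2.8.1.

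Identify worsening from a new AE record or from the SAE form. Where a record holds only one severity grade, query AEs that began before first dose and were ongoing at it, and do so before database lock.

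The cost is one extra flag in the AE dataset and possibly a few queries. No change to the visit schedule or the sample size is needed.

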3.1.2 Double-blind treatment period (Randomization through Week 12 pre-dose)

The Double-blind Treatment Period is defined as Randomization through Week 12 (prior to the Week 12 dose).

At the start of the Double-blind Treatment Period, eligible subjects will be randomized via Interactive Response Technology (IRT) in a 1:1 ratio to one of two treatment groups (secukinumab 300 mg or placebo). **Subjects must be randomized and receive their first dose of study treatment no later than 7 days after the FDG-PET/CT scan.**

- **Secukinumab:** secukinumab 300 mg (two s.c. injections of the secukinumab 150 mg dose) once weekly for five weeks (at Randomization, Weeks 1, 2, 3, and 4) followed by a dose after four weeks at Week 8 (last dose during Double-blind Treatment Period).
- **Placebo:** placebo (two s.c. injections of 150 mg secukinumab placebo per dose) once per week for five weeks (at Randomization, Weeks 1, 2, 3 and 4) followed by a dose after four weeks at Week 8 (last dose during Double-blind Treatment Period).

During the Double-blind Treatment Period, all subjects will attend study visits at Randomization, Weeks 1, 2, 3, 4, 8, and 12, and all doses of study treatment will be **self-administered at the study site**.

Assessments for the primary efficacy variable will be performed at Week 12 for both treatment groups **prior to** subjects receiving their Week 12 dose.

All subjects who discontinue study treatment prematurely for any reason before the end of Double-blind Treatment Period should return to the study site for the performance of the Visit 8/Week 12 End of Treatment 1 (EOT1) assessments. The EOT1 visit should be scheduled 28 days (± 7 days) after the last dose of study treatment.

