3.1.4 Open-label treatment period (Week 16 through Week 52)

[figure not shown]
All subjects who complete the Double-blind Induction Period will enter the Open-label Treatment Period. The Open-label Treatment Period is defined as Week 16 through Week 52. All subjects in

the Open-label Treatment Period will receive secukinumab 300 mg s.c. at four-week intervals beginning at Week 16 through Week 48 (last dose during the Open-Label Treatment Period).

Self-administration of the doses at Weeks 16, 24, 32, 40, and 48 will take place at the study site; the doses at Weeks 20, 28, 36, and 44 will be self-administered at home.

All subjects who discontinue study treatment prematurely for any reason before the end of the Open-label Treatment Period should return to the study site for the performance of the Visit 14/Week 52 End of Treatment 2 (EOT2) assessments. The EOT2 visit should be scheduled 28 days (± 7 days) after the last dose of study treatment.

Figure 3-1 Study design

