5.5.5 Permitted dose adjustments and interruptions of study treatment

Study treatment dose adjustments and/or interruptions are not permitted.

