5.5.9 Discontinuation of study treatment

Subjects may voluntarily discontinue study treatment for any reason at any time. They may be considered withdrawn if they state an intention to withdraw, fail to return for visits, or become lost to follow-up for any other reason. Subjects who prematurely withdraw from the study will not be replaced.

If discontinuation occurs for any reason during the study, the Investigator/qualified site staff must make every effort to determine the primary reason for a subject’s discontinuation from the study. This information will then be recorded on the End of Treatment eCRF for either the Double-blind Treatment Period (Visit 8/Week 12 EOT1), or the Double-blind Induction and Open-label Treatment Periods (Visit 14/Week 52 EOT2) as appropriate.

Study treatment must be discontinued and the subject withdrawn from the study if the Investigator on balance believes that continuation would be detrimental to the subject’s well-being. Study treatment **must** be discontinued under the following circumstances:

- Emergence of the following AEs: AEs that in the judgment of the Investigator/qualified site staff, taking into account the subject’s overall status, prevent the subject from continuing study treatment (for example, sepsis or serious infection);
- Any laboratory abnormalities that in the judgment of the Investigator/qualified site staff, taking into consideration the subject’s overall status, prevents the subject from continuing study treatment;
- Pregnancy (see [Section 6.5.6](#) and [Section 7.3](#));
- Ongoing use of any prohibited treatment, use of a prohibited treatment that results in an undue safety risk for the subject as per the Investigator’s clinical judgment, or receipt of a live virus vaccine during the study (as detailed in [Section 5.5.8](#));
- Emergency unblinding;
- Any other protocol deviation that results in a significant risk to the subject’s safety or significantly affects the validity of the study assessments.

Subjects who discontinue study treatment should undergo an end of study visit and then be discontinued from the trial.

- **Double-blind Treatment Period:** For subjects who discontinue study treatment prematurely before the end of the Double-blind Treatment Period, the Visit 8/Week 12 EOT1 assessments should be performed. **NOTE: Consultation with the Medical Monitor is required to**

determine if the FDG-PET/CT scan assessment should be performed during the discontinuation visit.

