## **2.3 Patient disposition, demographics and other baseline characteristics**

### **2.3.1 Patient disposition**

The number of subjects screened will be presented along with the reasons for screen failures for all subjects as specified in the screening phase disposition eCRF.

The number and percentage of subjects screened, randomized, completed study periods (treatment period 1 and treatment period 2), and discontinued the study prematurely including

the reason for discontinuation will be presented by overall and study periods for each treatment group for all screened subjects.

Patients withdrawing consent will be listed with reason for withdrawal.

The number and percentage of subjects with protocol deviations (see Appendix 5-5) will be tabulated by treatment and listed separately by treatment groups.

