### **Treatment groups for evaluation**

The summaries of evaluation will be reported for treatment period 1 and entire treatment period, respectively.

The following groups will be used for treatment period 1:

- Secukinumab 300mg
- Placebo

The following groups will be used for entire treatment period:

- Secukinumab 300mg
- Placebo / Secukinumab 300 mg

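### Non-serious AEs are tabulated only to 7 days after the last dose while most doses are 28 days apart, so an AE that ends treatment can fall out of the AE tables

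*SAP*

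**What the plan says.** SAP 2.8.1 counts AEs as treatment-emergent from the first dose to 7 days after the last dose, or 30 days if serious. Of later events it says that "those occurring after 7 days of last study treatment (30 days for SAEs) will be listed only". The summaries are by system organ class and preferred term. Under SAP 2.8, Treatment groups for evaluation, "The summaries of evaluation will be reported for treatment period 1 and entire treatment period, respectively". SAP 2.1.1.4 says that the last-dose date comes from the CRF; nothing there or in 2.8.1 says how the window works in the treatment-period-1 table.

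The dosing calendar is in the protocol. Section 3.1.2 has weekly doses from randomization to Week 4, then one at Week 8. Section 3.1.3 has weekly injections at Weeks 12 to 15 in both arms. Under 3.1.4 all subjects "will receive secukinumab 300 mg s.c. at four-week intervals beginning at Week 16 through Week 48".

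On stopping, Protocol 5.5.5 says "Study treatment dose adjustments and/or interruptions are not permitted", and 5.5.9 requires treatment to end for AEs judged to "prevent the subject from continuing study treatment". On collection, Protocol 3.1.2 says of early stoppers that "The EOT1 visit should be scheduled 28 days (± 7 days) after the last dose of study treatment", and Protocol 7.1 says "The occurrence of adverse events should be sought by non-directive questioning of the subject at each visit during the study".

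**The concern.** A 7-day tail fits weekly dosing. With four-weekly dosing it is a quarter of the interval, and the event can then decide its own cut-off. If the subject goes on to the next dose, the last dose moves forward and the event falls inside the window. If the event makes the subject stop, the last dose stays where it was and the event falls outside. The same applies to any non-serious AE late in the interval in a subject who stops for another reason. Because interruptions are not allowed, a subject cannot miss one dose because of an AE and resume later under the protocol.

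Safety and tolerability is a stated secondary objective, and the tables by treatment group are its main AE output. A tolerability table should not leave out an event because that event ended treatment. The affected data are collected, since early stoppers are seen about four weeks after the last dose and asked about AEs then. Protocol 9.5.2 describes the AE summaries without any 7-day limit, so the restriction comes from the SAP. With about 42 subjects per arm, one subject is 1/42 = 2.4 percentage points.

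**Working it through.** **Calendar.** Study day = 7 × week + 1, which matches the scheduled days in SAP Tables 1-1 and 1-2 (Week 4 = Day 29, Week 12 = Day 85, Week 52 = Day 365). Doses fall on Days 1, 8, 15, 22, 29, 57, 85, 92, 99, 106, 113 and then every 28 days to Day 337.

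**Check against the plan's own figure.** Protocol 5.5.4 gives 12, 8 and 18 injections for the three treatment periods. The calendar has 6, 4 and 9 doses; at two injections each that is 12, 8 and 18, an exact match.

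**Gaps between doses.** There are 18 gaps: 8 of 7 days and 10 of 28 days (8 × 7 + 10 × 28 = 336 days). This assumes that the sham injections at Weeks 13 to 15 count as study treatment.

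**Onset days whose tabulation depends on the next dose.**
- 7-day gap: the latest onset before the next dose is +6, so none.
- 28-day gap: +8 to +27 = 20 days; 20/28 = 71%.
- Double-blind period: after Day 29 the cut-off is Day 36, leaving Days 37–56; after Day 57 it is Day 64, leaving Days 65–84. Together 40/84 = 48%.
- Weeks 16 to 48: 8 gaps × 20 = 160 of 224 days.
- First dose to the Week 48 dose: (40 + 160)/336 = 200/336 = 60%.

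**Example.** A non-serious AE starts on Day 70. If the Week 12 dose is taken, it is tabulated. If the subject stops, the last dose is Day 57, the cut-off is Day 64, and it is only listed.

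**Completers.** Last dose Day 337 + 7 = Day 344. Days 345–365 are 21 days; 21/365 = 5.8%. This tail is open-label and does not touch the placebo comparison.

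**Serious events.** The latest onset in a nominal 28-day gap is +27, inside 30 days, so none is lost. The margin is thin: with the ±2-day visit windows, Week 4 on Day 27 and Week 8 on Day 59 are 32 days apart.

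**Days between the cut-off and the end-of-treatment visit.** With the visit at +21, +28 or +35 days, a 7-day cut-off leaves 14, 21 or 28 days untabulated; a 30-day cut-off leaves 0, 0 or 5.

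**The case against.** The best defence is that nothing disappears. Every affected event is listed by treatment group with severity, relationship, action taken and outcome. SAP 2.3.1 adds that "the reason for discontinuation will be presented by overall and study periods for each treatment group for all screened subjects", and notable vital signs are tabulated separately. In a trial of 84 subjects a careful reader can recover late stopping events from listings. Also, the examples of stopping AEs in Protocol 5.5.9 (sepsis, serious infection) would ordinarily be serious and so covered to 30 days. All of this stands and limits the consequence. But the disposition table gives a reason, not an AE term, and action taken is only listed, so no planned table would name a late, non-serious AE that ended treatment.

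The 7 days may come from the safety master analysis plan that the SAP cites. That plan is not available, so the rationale cannot be judged; the effect of the rule on this calendar is the same either way.

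Three stronger readings are tempting and are not supported:
- *The tables favour secukinumab.* Dosing days are the same in both arms to Week 12, so any bias depends on how often AEs cause stopping in each arm, and the documents give no such rates.
- *Days 65–85 are lost for everyone in the treatment-period-1 table.* That needs the last dose to mean the Week 8 dose, from an exposure note in Protocol 9.3 that the SAP does not link to AEs. The literal reading is the last dose in the study. The SAP's silence is a gap to close, not evidence for the Week 8 reading.
- *The SAP contradicts itself because it uses last dose + 84 days elsewhere.* Those definitions concern assessments and exposure; they are not a rival AE rule.

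**Conclusion.** The point holds for non-serious AEs. On the literal text, an event starting 8 to 27 days after a four-weekly dose enters the tables only if a later dose is taken. The untabulated tail for completers is a lesser part of the same rule.

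The day counts rest on the nominal schedule and on the last dose meaning the last dose in the study. They must not be read as saying that 48% or 60% of AEs go missing: they apply only to non-serious AEs in subjects who stop, and subjects who continue lose nothing before Day 345. No subject count can be given. The primary endpoint is unaffected.

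This ranks between minor and should-fix: selective by construction and cheap to correct, but with the data kept in listings and serious events covered on schedule.

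**What to change.** In SAP 2.8.1:
- Keep the window for serious events at no less than last dose + 30 days, and extend the non-serious window to match. End it at the latest of last dose + 30 days, the end-of-treatment visit and the treatment discontinuation date.
- For the treatment-period-1 table, include onsets from the first dose to before the Week 12 dose. For subjects who take no Week 12 dose, use the window above with no cap at Day 85.
- State that the last dose means the last dose in the study.

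On the nominal schedule this leaves 0 of the 40 double-blind days and 0 of the 200 days dependent on the next dose, and completers are covered to 337 + 30 = Day 367.

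Two simpler period-1 endings should be avoided. Ending at the EOT1 visit would drop serious events that are now tabulated: with last dose Day 29 and EOT1 at +21 days (Day 50), Days 51–59 would go. A cap at Day 85 would recreate the asymmetry: the Week 12 visit may fall on Day 87 and the dose up to 7 days after the scan, so on Day 94, and an AE on Days 86–93 would count only if the dose followed.

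The cost is SAP wording and one derivation flag, with no new data. AE counts rise slightly, and a few events may arise after a subject has moved to other treatment. In the period-1 table, stoppers after Week 8 may be followed a few days longer than continuers: to Day 87 (57 + 30), or Day 92 if EOT1 is at +35 days, against nominal Day 85.
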